### **Sensitivity Analysis**

The primary endpoint analysis will be repeated using the PP and Safety Populations as sensitivity analyses.

A complete case analysis, using patients with completed clinical status assessments at Day 7, will be presented.

An analysis of the primary endpoint, using all data collected regardless of prohibited medication use, will also be conducted.

A worst-case scenario will be conducted as an additional sensitivity analysis, counting all subjects with missing data at Baseline (Day 1) or Day 7 as failures.

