9.1 Determination of Sample Size

A subject is determined to reach the primary endpoint “stabilization or improvement in clinical status defined as maintenance or improvement by one category on a 6-category clinical status scale on Day 7” if the clinical status category on Day 7 is not worse than the clinical status category at Baseline (Day 1 prior to IMP infusion).

The study is determined to be successful if the proportion of subjects randomized to the IVIG group who reach the primary endpoint is significantly greater than the proportion of subjects randomized to the placebo group who reach the primary endpoint.

High-dose IVIG is used as a therapeutic option for severe-type COVID-19 (37) and given the severity of the population in our study as compared to the reference study, we assume 80% of subjects in the IVIG group and 60% of subjects in the placebo group will meet the primary endpoint.

With overall two-sided significance level of 0.05 when testing the difference in proportions between two treatment groups using normality approximation, 176 subjects (n=88 for each treatment group) will provide statistical power of at least 80%. Assuming a drop-out rate of 15% from Baseline (Day 1) relative to the efficacy assessment date at Day 7 after first dose for both groups, a final sample size of 208 (n=104 for each treatment group) is sufficient to maintain the minimum statistical power as 80%.

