9.2.5 Handling of Missing Data

In support of the primary and key secondary endpoints of stabilization or improvement in clinical status the following imputation methods will be used. For subjects with clinical status assessment at Baseline (Day 1) and at least one non-missing post-baseline clinical status assessment, last observation carried forward (LOCF) will be used to

impute the missing data at Day 7. However, if there is available data that otherwise indicates events such as death, ECMO or IMV, ICU admittance, occurred after the last non-missing clinical status assessment but on or prior to Day 7, the clinical status will be imputed according to the worst-case of either the LOCF or the clinical information available. Subjects with missing data at Baseline (Day 1) will be imputed as failure. Subjects with no post-baseline clinical status assessment on or prior to Day 7 will be imputed as failure.

Sensitivity analyses will be implemented by assuming all failure (worst case scenario) if subject has missing data at Baseline (Day 1) or Day 7, and where subjects with missing data are excluded.

Missing data for the outcome of clinical status at Day 14 will be imputed in the same fashion as in primary endpoint.

For the key secondary endpoint involving severe progression (ECMO, IMV, death, ICU admittance), subjects who withdrew early from study prior to Day 33 without evidence of events will be treated as not having the event. Sensitivity analyses will be conducted (1) treating them as failures (having the event at their last study visit) and (2) excluding them from the analyses. An additional analysis of these endpoints will be provided, treating prohibited medication use prior to Day 33 as an event, as well as allowing for status (event or success) without regard to prohibited medication use.

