##### **4.1 Missing Data**

The latest patient status available prior to Day 7 will be used to determine clinical status in the absence of a clinical status assessment. If a death date is prior to Day 7, clinical status at Day 7 will be identified as a 6. Otherwise, if a subject's last status reflects that they were in the ICU and receiving ECMO and/or IMV, clinical status will be imputed as a 5. Otherwise, if a subject's last status reflects that they were in the ICU and not receiving ECMO and/or IMV, clinical status will be imputed as a 4. If the LOCF clinical status value for a patient is higher than these imputed values or if a subject status cannot be derived based on available information on ECMO, IMV, or ICU status, the last observation carried forward (LOCF)

will be used to impute patient values. Subjects with no post-baseline clinical status assessment, or prohibited medication use, on or prior to Day 7 will be imputed as failure.

An imputation analogous to the primary endpoint will be performed for the secondary endpoint of clinical status at Day 14.

For the secondary endpoint length of hospitalization, Subjects who are still hospitalized as of Day 33, subjects with missing end dates due to withdrawal, subjects with unusable end dates due to prohibited medication use, or those who died on/prior to Day 33 will be censored at Day 33. Discharge occurring on or after the start date of prohibited medication use will not be considered an event.

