#### **4.6 Reporting Timeframe of Measurement for Analysis**

For analyses of primary and secondary efficacy endpoints, including clinical status and RT-PCR, the latest observation within any given study day will be used. If the observations for the Day 7 visit falls outside of the 24-hour window of the study day or the Day 14 visit falls outside of the 48-hour window of the study day, the observation will be considered as missing and the imputation described in Section 4.1 will apply as appropriate. Otherwise, unless specifically stated otherwise, analyses will be conducted based on nominal visits.

For summary analyses of efficacy assessment, including oxygenation, oxygen saturation, modified Borg Dyspnea Scale and McGill Quality of Life Single-Item Scale (MQoL-SIS) and safety parameters (including vital signs, clinical laboratory evaluations and chest CT/chest X-ray findings), the latest observation within the study day during treatment period will be used. No imputation will be made for these assessments.

For safety analysis with adverse events, the observation with highest severity within the study day during treatment period will be used. No imputation will be made.

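### The primary endpoint's 'worst-case' sensitivity analysis fails missing subjects in both arms, so it does not bound the treatment difference, and no planned analysis lets outcomes among the missing differ by arm

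*SAP*

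**What the plan says.** The primary endpoint is success at Day 7, meaning clinical status no worse than at Baseline. It is tested in the ITT population by CMH stratified by age (Protocol 9.2.3.2; SAP section 13). Missing Day 7 status is handled in three ways:

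- **Primary analysis (SAP 4.1):** "The latest patient status available prior to Day 7 will be used to determine clinical status in the absence of a clinical status assessment". Known death, ECMO/IMV or ICU status is used, and LOCF otherwise. A subject with no Baseline value, or with no post-baseline assessment by Day 7, is a failure.
- **Complete case (SAP section 13, Sensitivity Analysis):** "A complete case analysis, using patients with completed clinical status assessments at Day 7, will be presented". Protocol 9.2.5 also plans an analysis that excludes subjects with missing data.
- **All failure:** the SAP has "A worst-case scenario will be conducted as an additional sensitivity analysis, counting all subjects with missing data" at Baseline or Day 7 as failures. Protocol 9.2.5 has "assuming all failure (worst case scenario) if subject has missing data at Baseline (Day 1) or Day 7".

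None of these rules distinguishes the arms. The other sensitivity analyses change the population (PP, Safety) or disregard prohibited medication. Neither document plans a tipping-point, delta-adjusted or arm-specific analysis for this endpoint.

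Two further provisions affect how much data may be missing. Protocol 9.1 has "Assuming a drop-out rate of 15% from Baseline (Day 1) relative to the efficacy assessment date at Day 7". SAP 4.6 says of a Day 7 observation outside its 24-hour window that "the observation will be considered as missing and the imputation described in Section 4.1 will apply as appropriate".

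**The concern.** The trial is judged on a difference between two proportions. Setting every missing subject to failure gives the lowest possible success rate in each arm. The lowest possible difference needs missing Octagam subjects to fail and missing placebo subjects to succeed. The planned rule therefore does not deliver for the treatment effect what its label suggests, and it can move the estimate in Octagam's favour when more placebo subjects are missing.

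A gap remains when the three approaches are taken together. Subjects may be missing for different reasons in the two arms, for example poor tolerance on one side and early recovery on the other. The outcomes of the missing would then differ by arm, and nothing planned explores that. At stake is the robustness statement attached to the primary result, not the primary test itself.

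**Working it through.** **Inputs.** Protocol 9.1 gives 80% vs 60% success, 88 evaluable and 104 randomised per arm, 15% drop-out and two-sided 0.05. The number actually missing at Day 7 is not given, so it is varied. The age split is not given either, so the tests are unstratified and approximate the planned CMH test.

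**Plan's own figures.** 88/0.85 = 103.5, rounded up to 104 per arm, 208 in total. Power at 88 per arm is Φ[(0.20 − 1.96·√(2·0.7·0.3/88)) / √((0.16 + 0.24)/88)] = Φ(0.958) = 83%. Both agree with the protocol, so the sample size is not in question.

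**Formulas.** Let p be the success rate among observed subjects and m the fraction missing.

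- All-failure difference: (1 − m_Oct)·p_Oct − (1 − m_Pla)·p_Pla.
- Arm-opposed lower bound: the all-failure difference minus m_Pla.
- Test: z = difference / √(p̄(1 − p̄)(1/n1 + 1/n2)), two-sided, where p̄ is the pooled rate.

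The planned analysis therefore stops short of the true lower bound by exactly the fraction missing on placebo.

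**At the 15% allowance (16 missing per arm).** Observed successes are 0.8 × 88 ≈ 70 and 0.6 × 88 ≈ 53.

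| Analysis | Octagam | Placebo | Difference (points) | p |
|---|---|---|---|---|
| Complete case | 70/88 | 53/88 | 19.3 | 0.005 |
| All failure (planned) | 70/104 | 53/104 | 16.3 | 0.017 |
| Octagam missing fail, 3 of 16 placebo succeed | 70/104 | 56/104 | 13.5 | 0.047 |
| Octagam missing fail, 4 of 16 placebo succeed | 70/104 | 57/104 | 12.5 | 0.065 |
| Arm-opposed extreme | 70/104 | 69/104 | 1.0 | 0.88 |

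For the planned row, p̄ = 123/208 = 0.591, the standard error is √(0.591 × 0.409 × 2/104) = 0.0682, and z = 0.1635/0.0682 = 2.40. The Miettinen-Nurminen 95% interval is 3.0 to 29.2 points.

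A milder point on the boundary: if 8 of 16 missing Octagam subjects succeed, significance is lost when 12 of 16 missing placebo subjects do (78/104 vs 65/104, p=0.052).

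**Dependence on the amount missing (equal in both arms).**

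| Missing per arm | All failure | Arm-opposed extreme |
|---|---|---|
| 2 | 20.2 points, p=0.002 | 18.3 points, p=0.004 |
| 5 | 19.2 points, p=0.003 | 14.4 points, p=0.025 |
| 6 | 18.3 points, p=0.006 | 12.5 points, p=0.052 |
| 10 | 18.3 points, p=0.006 | 8.7 points, p=0.18 |
| 16 | 16.3 points, p=0.017 | 1.0 point, p=0.88 |

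Success counts are rounded to whole subjects, which is why the 6 and 10 rows share an all-failure difference.

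**Unequal missingness (assumed splits, 32 missing in total).**

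| Missing Octagam / placebo | Complete case | All failure |
|---|---|---|
| 10 / 22 | 75/94 vs 49/82: 20.0 points, p=0.004 | 75/104 vs 49/104: 25.0 points, p=0.0002 |
| 20 / 12 | 67/84 vs 55/92: 20.0 points, p=0.004 | 67/104 vs 55/104: 11.5 points, p=0.09 |

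The same rule raises the estimate in the first row and removes significance in the second. In the first row the arm-opposed extreme is 75/104 vs 71/104, 3.8 points, p=0.54.

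**The case against.** **The all-failure analysis is a real stress test in one direction.** A reader might infer that it can never overturn the result. That holds only when the arms lose similar numbers; with 20 missing on Octagam and 12 on placebo it does remove significance. This objection stands, and the point is limited to differing outcomes among the missing.

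**The 15% is an allowance.** A reader might infer that the sponsor expects 15% of subjects to lack Day 7 data. Protocol 9.1 only assumes that figure for sizing, and several provisions work against it:

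- Day 7 falls early, mostly in hospital, with a one-day tolerance (Protocol 6.1, 6.1.8).
- Clinical status is collected by telephone on Day 7 for subjects discharged by Day 5 (6.1.6).
- Follow-up continues after infusions stop for prohibited medication or severe hypersensitivity (4.2, 5.4).
- Deaths before Day 7 are scored from the death date (SAP 4.1).

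This also stands. In the other direction, the window rule in SAP 4.6 adds some missing values.

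**The arm-opposed extreme is implausible.** It needs 0 of 16 missing Octagam subjects to succeed and 16 of 16 on placebo, against 80% and 60% among those observed. It also disregards status recorded on Days 1 to 4 and oxygenation changes recorded between visits (Protocol 6.1.2, 7.2.2). Agreed: the tipping point is the more useful figure.

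**The label is partly a matter of wording.** Both documents state the rule in the same sentence as the label, and the analysis is no criterion for success. That lowers the weight of the point but does not fill the gap.

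**Conclusion.** The concern holds in a limited form. The planned worst case bounds each arm's success rate, not the treatment difference, and no planned analysis examines whether missing Octagam subjects did worse than missing placebo subjects.

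The size depends on a quantity the documents do not give. At the planned effect and equal missingness, the arm-opposed extreme leaves the result significant with 5 missing per arm, borderline with 6 and lost with 10. At 16 per arm, with every missing Octagam subject failing, four placebo successes among the missing are enough to lose it. All p-values are unstratified and assume exactly the planned rates among observed subjects.

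A reader might go further and conclude that missing data would decide this trial, or that the primary analysis is unsound. The documents support neither. Missingness may prove small, the primary test is unaffected, and the all-failure analysis is legitimate under an accurate name. This is an inexpensive improvement to the robustness plan.

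**What to change.** 1. Keep the analysis in SAP section 13 and Protocol 9.2.5, but rename it *missing = failure in both arms*.
2. Before unblinding, add to SAP section 13 a two-way tipping-point table. Its axes are the number of missing subjects counted as successes on Octagam and on placebo, each from 0 to all. Known deaths, ECMO/IMV and other documented failures stay fixed as failures.
3. Report the boundary where the age-stratified CMH p-value crosses 0.05, with the arm-opposed corner marked as the extreme. Since the test is stratified, state how imputed successes are allocated to the two age strata.
4. Show the number missing at Day 7 by arm and reason beside the table, so that the reader can judge which cells are plausible.

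The cost is a short SAP paragraph and one table from data already collected, with no change to the primary test or the sample size. The downside is that the robustness statement may look less favourable. If few subjects are missing, the table will show that the result is safe.

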#### 14. Analysis of Secondary Endpoints

The analyses for secondary endpoints will be based on the ITT Population. The hypothesis testing with p-value assessments for secondary endpoints at designated timepoints will be implemented for confirmatory purpose after statistical significance is claimed from the primary endpoint. The following secondary endpoints will be analyzed by hierarchical procedure in the order specified below with overall 2-sided type I error of 0.05:

1. Length of hospital stay (time to discharge) through Day 33
2. Proportion of subjects with maintenance or improvement by at least one category on the 6-point clinical status scale on Day 14.
3. Cumulative duration of IMV through Day 33
4. Proportion of subjects with severe progression defined as requiring ECMO, IMV and/or have died through Day 33
5. Length of time in ICU from randomization through Day 33
6. Mortality rate through Day 33

The hierarchical testing procedure will stop when one of the endpoints cannot demonstrate statistical significance, i.e. as soon as the first statistical test yields a p-value  $\geq 0.05$ . If this happens, the subsequent endpoints will not be tested.

Length of hospitalization is defined as (date of discharge – randomization date + 1). Subjects who are still hospitalized as of Day 33, subjects with missing end dates due to withdrawal, subjects with unusable end dates due to prohibited medication use, or those who died on/prior to Day 33 will be censored at Day 33. The median time to discharge and associated 95% CI for each treatment arm will be estimated using the Kaplan-Meier method. Comparisons between treatment arms will be performed using a log-rank test, stratified by age category. A rate ratio and associated 95% CI, equivalent to a hazard ratio from a Cox proportional hazard model stratified by age, will also be presented.

Proportion of subjects that stabilized or improved at Day 14 is defined as per the primary endpoint and hypothesis testing for proportions will be conducted as described for the in the primary endpoint section.

Cumulative duration on IMV through Day 33 and is defined as (IMV end date – IMV start date + 1). Subjects who do not require IMV will have a duration set to 0. Subjects who die on or prior to Day 33 or are still on IMV at Day 33, will have a duration set to their actual/projected Day 33 date for the IMV end date, so long as prohibited medication was not administered. If IMV end date is missing but subject is discharged from ICU or hospital, then IMV end date will be set to the earlier of the ICU or hospital discharge date. Otherwise, subjects without usable IMV end date information due to withdrawal or prohibited medication use will use a projected Day 33 date for the IMV end date. Comparisons between

treatment arms will be performed using a stratified Wilcoxon-Mann-Whitney (van Elteren) test with age category as a stratification factor.

Proportion of subjects with severe progression will be defined as the proportion that require ECMO, IMV or died prior to Day 33. For this analysis, subjects who use prohibited medication prior to the earliest of progression or Day 33 will not be included in analyses. Hypothesis testing for this endpoint will be conducted as described for the primary endpoint.

Length of time in ICU from randomization through Day 33 includes number of days spent in the ICU from randomization through Day 33 and is defined as [ICU discharge date – (later of ICU admittance date, randomization date) + 1]. Subjects who are not admitted to the ICU will have a duration set to 0. Subjects who die on or prior to Day 33 or are still in the ICU at Day 33, will have a duration set to their actual/projected Day 33 date for the discharge date, so long as prohibited medication was not administered. If ICU discharge date is missing but subject is discharged from hospital, then ICU discharge date will be set to hospital discharge date. Otherwise, subjects without usable ICU end date information due to withdrawal or prohibited medication use will use a projected Day 33 date for the ICU end date. Comparisons between treatment arms will be performed using a stratified Wilcoxon-Mann-Whitney (van Elteren) test with age category and baseline ICU status (In ICU at baseline versus not in ICU at baseline) as stratification factors.

Mortality rate is defined as the proportion of subjects who have died on or prior to Day 33. For this analysis, subjects who use prohibited medication prior to the earliest of death or Day 33 will not be included in analyses. Hypothesis testing will be performed as described for the primary endpoint.

Key secondary endpoints which demonstrate statistical significance will be analyzed by subgroups including sex (male/female), race, ethnicity, geographic region, and disease severity (according to the definitions in the eCRF). All key secondary endpoints will be analyzed by age using testing analogous (unstratified) testing methodology to the specified analyses. Length of time in ICU from randomization through Day 33 will also be analyzed by baseline ICU status. Sensitivity analyses, using all available data, regardless of prohibited medication usage, will be conducted where applicable. The descriptive analyses for the following other secondary endpoints will be based on the primary efficacy analysis (e.g. CMH) method:

- Proportion of patients whose results of reverse transcription polymerase chain reaction (RT-PCR) for SARS-CoV-2 from nares/throat swab and/or sputum and/or lower respiratory tract sample are “Not Detected” on Day 7
- Proportion of subjects admitted to the ICU from randomization through Day 33
  - Only admittance (new or returning) post-randomization will qualify as an event
  - Analyses will be stratified additionally by baseline ICU status
  - If expected event counts do not satisfy CMH testing criteria, baseline ICU status will be removed from analysis as a first step in analysis update
- Proportion of subjects with improvement on Days 7, 14, 21, 33

- Proportion of subjects requiring IMV by Day 33.

The descriptive analyses for the following, other secondary endpoints will be based on the Kaplan-Meier analysis of length of hospitalization:

- Time to recovery through Day 33 where recovery is defined as a clinical status of 1 or 2
- Time to first improvement in clinical status through Day 33

These secondary endpoints will also be analyzed by age category.

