4.1.2 Exclusion Criteria

Subjects who meet any of the following criteria are *not* eligible for the study:

1. Existence of other evidence that can explain pneumonia including but not limited to: Influenza A virus, influenza B virus, bacterial pneumonia (as suggested by the combined clinical picture, radiological findings and known laboratory results [eg, elevated procalcitonin >0.5 ng/mL and concomitant neutrophilia]), known fungal pneumonia, suspected fungal pneumonia based on compromised immune system with a history of past fungal infections, noninfectious causes, etc.
2. Known history of serious allergic reactions, including anaphylaxis, to IVIG or its preparation components.
3. Subjects with a history of thromboembolic event (TEE) within the last 12 months, such as deep vein thrombosis, pulmonary embolism, myocardial infarction, ischemic stroke, transient ischemic attack, peripheral artery disease (Fontaine IV).

4. Subjects with an underlying medical condition that can lead to hypercoagulable states and hyperviscosity such as antithrombin III deficiency, Factor V Leiden, Protein C deficiency, antiphospholipid syndrome, and malignancy.
5. Known history of selective IgA deficiency with antibodies against IgA.
6. Subjects with conditions such as human immunodeficiency virus (HIV) infection, known acute or chronic hepatitis B or C (HBsAg positive or HCV RNA PCR positive or currently treated with antivirals), pulmonary fibrosis, heparin induced thrombocytopenia (HIT), and moderate to severe renal dysfunction (per investigator discretion based on estimated glomerular filtration rate [eGFR] <59 mL/min/1.73 m², as defined by KDIGO Clinical Practice Guideline):
 - Moderately reduced GFR (G3a): GFR = 45 to 59 ml/min/1.73 m²
 - Moderately reduced GFR (G3b): GFR = 30 to 44 ml/min/1.73 m²
 - Severely reduced GFR (G4): GFR = 15 to 29 ml/min/1.73 m²
 - Kidney failure (G5): GFR <15 ml/min/1.73 m².
7. Currently requiring invasive mechanical ventilation or having received invasive mechanical ventilation in the last 30 days.
8. Known clinically significant preexisting lung, heart, neuromuscular or other disease that, in the investigator's opinion, would impact the subject's ability to complete study or may confound the study results.
9. Body weight > 125kg.
10. Women who are pregnant or breast-feeding.

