Cumulative duration in ICU will be imputed similarly, unless a patient has a useable discharge date (e.g. not occurring prior to prohibited medication use); in this case, the ICU discharge date will be set to the hospital discharge date. If a subject's last assessment identifies that IMV was used (and has no usable end date), the date on which it is no longer used will be assumed Day 33 unless the subject is discharged from the hospital prior to Day 33. If this occurs, the hospital discharge date will be used. IMV end dates will be imputed similarly, assuming that IMV ceases at the time of ICU discharge. Hospitalization, ICU, and IMV end dates for subjects who died prior to Day 33 during these events (e.g. after ICU admission or IMV initiation) will result in assumed end dates of Day 33 for endpoint analyses, so long as prohibited medication was not administered. Any dates on or after the start date of prohibited medication use will be considered unusable for imputation purposes; ongoing hospitalization, ICU, or IMV at the time of medication use will default to extrapolation to Day 33.

For the key secondary endpoint involving severe progression (ECMO, IMV, and death), subjects who withdrew early from study prior to Day 33 without evidence of events will be treated as not having the event. Sensitivity analyses will be conducted (1) treating them as failures (having the event at their last study visit) and (2) excluding them from the analyses. An additional analysis of these endpoints will be provided, treating prohibited medication use prior to Day 33 as an event, as well as allowing for status (event or success) without regard to prohibited medication use.

The outcomes for safety assessment and for additional efficacy analysis as well as exploratory endpoints will not be imputed if data is missing.

Please also refer to the more detailed descriptions in sections 12 to 18 of this SAP for additional details on the handling of missing data for particular endpoints and analyses.

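### A death by Day 33 without ventilation scores 0 IMV days, the best possible value, so the confirmatory test of IMV days does not respond to such deaths (ICU days shares the property but is better protected)

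*SAP*

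**What the plan says.** Cumulative duration of IMV is key secondary endpoint 3 and length of time in ICU is endpoint 5. Each is compared by a van Elteren test on days, stratified by age category and, for ICU days, also by baseline ICU status.

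SAP 14 and Protocol 9.2.3.2 give the same zero rules: "Subjects who do not require IMV will have a duration set to 0" and "Subjects who are not admitted to the ICU will have a duration set to 0". The next sentence of each rule sets the end date to Day 33 for subjects who die by then. SAP 4.1 words that extension as one for "Hospitalization, ICU, and IMV end dates for subjects who died prior to Day 33 during these events", with the start of IMV or ICU admission as its examples.

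For hospital stay, "those who died on/prior to Day 33 will be censored at Day 33", so a death is never counted as a discharge.

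The order of testing in SAP 14 is hospital stay, Day 14 status, IMV days, severe progression, ICU days, mortality, all after the Day 7 primary. "The hierarchical testing procedure will stop when one of the endpoints cannot demonstrate statistical significance".

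Nobody is ventilated at entry: exclusion 7 in Protocol 4.1.2 bars anyone "Currently requiring invasive mechanical ventilation or having received invasive mechanical ventilation in the last 30 days".

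**The concern.** Deaths on the ventilator or in the ICU are carried to Day 33 and so rank among the worst durations. Deaths that never reached either get the best value. Because no one enters on IMV, every death without later IMV is affected. A death in the ICU on non-invasive support counts towards ICU days but scores 0 for IMV days, so IMV days is the more exposed of the two.

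At stake is what a win on IMV days can be said to show. It is tested before severe progression and mortality, the two endpoints that count these deaths directly, and a later failure in the sequence does not withdraw a claim already made. The sensitivity analyses that SAP 14 plans for these endpoints concern prohibited medication. None changes the score of a death outside IMV or ICU.

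**Working it through.** **The text.** Duration is end date minus start date plus 1. A subject never ventilated has no start date, so the Day 33 end date has nothing to attach to and the zero rule applies. SAP 4.1 confirms this by tying the extension to deaths during the event. The tie follows from the wording alone.

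**Sample size used.** The documents give no power figure for IMV days or ICU days. The per-arm number comes from Protocol 9.1: 88/0.85 = 103.5, so 104 per arm, which reproduces the stated 208.

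**Test statistic.** With weight w = 1/(N+1) in each stratum, T = Σ w[R − n₁(N+1)/2], where R is the IVIG rank sum. Var(T) = Σ w² · n₁n₀/(N(N−1)) · Σ(r − r̄)², with midranks for ties.

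**Why it cannot move.** If 10 of 104 IVIG subjects are ventilated, the other 94 score 0 whether none or 15 of them died. The scores, and hence T and p, are identical.

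**Worked example, IMV days (all counts assumed).** Age strata of 70 and 34 per arm. Ventilated: 10+10 placebo v 5+5 IVIG, evenly spaced over 8 to 28 days. Deaths without IMV: 1+4 placebo, and 0+0, 1+4, 3+7 or 5+10 IVIG. Under worst rank these deaths are placed above every duration.

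| IVIG deaths without IMV (placebo 5) | Plan scoring, p | Worst rank, p |
|---|---|---|
| 0 | 0.048 | 0.004 |
| 5 | 0.048 | 0.096 |
| 10 | 0.048 | 0.59 |
| 15 | 0.048 | 0.62 |

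In the last row both arms have 25 subjects with IMV or death (10+15 v 20+5), but more of those on IVIG are deaths, so the direction turns against IVIG.

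**ICU days (assumed; stratified by baseline ICU only).** With 20 per arm in ICU at baseline with identical days, new ICU stays 22 v 10 and 5 placebo deaths without ICU, plan scoring gives p=0.057 in all four cases. Worst rank gives 0.007, 0.096, 0.48 and 0.85.

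**Effect of the earlier steps.** A simulation of 4,000 trials per case, unstratified, 104 per arm, required IVIG to win the Day 7 primary, hospital stay and Day 14 status before IMV days. Assumed: IMV in 20% v 10% (placebo v IVIG), starting on Days 2 to 14, with 40% of ventilated subjects dying; deaths without IMV on Days 2 to 14; exponential length of stay.

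| Deaths without IMV, placebo v IVIG | Milder deterioration | Mean stay, days | IMV-days win, plan | Worst rank |
|---|---|---|---|---|
| 5 v 15% | 20 v 20% | 10 v 10 | 0% | 0% |
| 5 v 15% | 20 v 10% | 10 v 8 | 2% | 0% |
| 5 v 15% | 20 v 0% | 10 v 6 | 21% | 2% |
| 5 v 10% | 30 v 10% | 12 v 7 | 33% | 8% |

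If the deaths are spread over Days 2 to 33 (3,000 trials), the last two rows become 30 v 1% and 41 v 9%. In the table's last two rows, 18 of the 21 points and 23 of the 33 points then stop at severe progression, with the IMV-days claim already made.

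**The case against.** The strongest reply is that each rule follows its own measure. A patient who died in hospital was not discharged, one who died on a ventilator was ventilated, and one never ventilated had 0 days of ventilation. Death is carried by endpoints 4 and 6, and turning IMV days into a composite with death is a choice of estimand. This stands as an argument against forcing a redefinition. It does not remove the need to say what a win leaves out.

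The practical effect is also limited:

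- A death by Day 7 or Day 14 is a failure at the corresponding earlier step, and any death by Day 33 is a non-discharge in hospital stay.
- SAP 13 and 17 give stabilized-or-improved proportions at Days 21 and 33, and SAP 16 tabulates fatal adverse events, so an excess of deaths would be visible.
- In every simulated case IVIG truly halves IMV use. A win is incomplete as a description of benefit; it is not false for the stated measure.
- The large gaps need several assumptions at once: deaths without IMV double or triple while other deterioration falls sharply.

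A reader might infer more than the documents support:

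- **That the tests ignore deaths in general.** They do not. A death after a late start of IMV is discounted but still ranks worse than every subject at 0. With 20 v 20 ventilated and ten extra deaths in one arm, p is 1.00 if those deaths score 0 days, 0.20 at 4 to 6 days, 0.18 at 10 and 0.057 at 32 to 34.
- **That a wrong ICU-days claim has been shown.** It has not. The example's 0.057 is not a win, severe progression must be won first, and subjects in ICU at baseline are unaffected.
- **That every version of the IMV example is a win.** Only the two-strata version is. Without strata, plan scoring gives 0.0501, which fails.

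**Conclusion.** The point holds: deaths by Day 33 without IMV tie with the best outcome in the confirmatory test of IMV days, and the test does not respond to them. ICU days has the same property for deaths without ICU, with better protection from its place in the sequence.

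The tie is certain from the text. Its size is not, because the documents give no rate of such deaths and every count above is assumed. With no other IVIG benefit, the chance of a misleading IMV-days claim after the earlier steps is about zero. It becomes material (21 to 33% under plan scoring, against 2 to 8% under worst rank) only where IVIG clearly helps elsewhere while deaths without IMV rise. This should be fixed before unblinding. It does not undermine the trial's primary analysis.

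**What to change.** In SAP 4.1 and 14, before unblinding:

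1. State that in the main analysis a death by Day 33 without IMV scores 0 IMV days, and a death without ICU scores 0 ICU days.
2. Pre-specify for both endpoints a worst-rank van Elteren analysis with the same strata, in which every death by Day 33 ranks worse than any survivor, regardless of prohibited medication use. Define this as a rank above the largest possible duration. A fixed 34 days is not safe, because the rules use an actual or projected Day 33 date and Protocol 6.1.8 allows the Day 33 visit up to 3 days late (33 + 3 = 36).
3. Require that this analysis be reported beside any claim on IMV days or ICU days, with deaths with and without IMV or ICU shown by arm.
4. Reconcile SAP 14 with SAP 4.1 for a subject who came off IMV or left the ICU and died later. SAP 14 appears to run the end date to Day 33; SAP 4.1 refers to deaths during the event.

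The cost is one extra analysis per endpoint and some SAP text, with no new data and no protocol amendment. A claim may look less favourable. The worst-rank analysis will also count deaths after prohibited medication, which endpoints 4 and 6 exclude, and the report should say so.

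Making worst rank the main analysis is optional. It would need a protocol amendment, because Protocol 9.2.3.2 defines both endpoints, and it would overlap endpoints 4 and 6. It also loses power when such deaths are equal in both arms: in the unstratified example at 5 v 5 deaths, p=0.050 becomes 0.098, and in the simulation at 5 v 5% the chance of a win falls from 43% to 34%. If IVIG prevents these deaths (5 v 2%), it gains power, from 49% to 62%.
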